5.2. Specimen Repository and Destruction

Some of the specimens collect under this protocol would be stored for repository. Based on the clinical presentation and laboratory data, the researchers will determine further testing to be done on specimens from participants who are willing to allow storage of specimens for use in future studies of infectious disease. Upon this evaluation, researchers will develop a new protocol. Specimen will be maintained for further laboratory testing for up to 5 years after the study is completed. After 5 years, with the decision of Steering Committee and Governing Board, specimens in the INA-RESPOND specimen repository in NIH RD Jakarta, will either be destroyed, or after IRB approval, transferred to another existing protocol or a repository. The used and destruction of the archived specimens in the future, will be determined per INA-RESPOND SOP of Specimen Ownership, Access, and Use (see appendix C).

6. DATA MANAGEMENT AND ANALYSIS

6.1. Data Management

Participants' data will be coded with a unique identifier that does not contain any information capable of linking the data to the study participants. A code that links the unique identifier with the study participants will be kept in a locked file cabinet in a secure room. Only authorized study personnel will have access to the code and the data. Data will be keyed and tracked using the OpenClinica.

Data will be periodically sent to the INA-RESPOND Central Data Management Center. Site and national data will be analyzed by all investigators. The investigator is responsible for ensuring that the data collected is complete, accurate and recorded in a timely manner. Following each study visit, the investigator or designated site staff member will upload the completed Case Report Form (CRF) to INA-RESPOND EDMS. The data will then be entered into the database and reviewed for completeness and accuracy. The study team will be notified of any discrepancies for clarification.

The study team should also complete accurate source documentation to support the data collected on the CRF. Source documents include all recordings of observations or notations of clinical activities and all reports and records necessary for the evaluation and reconstruction of the clinical study. Source documents include, but are not limited to, the participant's medical records, laboratory reports, X-ray(s), radiologist reports, participant progress notes, pharmacy records and any other similar reports or records of procedures performed in accordance with the protocol.

It is not acceptable for the CRF to be the only record of the participant's participation in the study and participant progress should also be recorded in the participant medical records. This is to ensure that anyone who would access the participant's medical records has adequate knowledge that the participant is participating in a clinical study.

Any document that acts as a source document (the point of the initial recording of a piece of data) should be signed and dated by the person recording or reviewing the data for issues of medical significance (for example the review of laboratory reports). Persons signing the source documents should be listed as a site staff member.

6.2. Analysis

An interim analysis will be conducted every 3-6 months to discuss the operation and challenges of the screening and enrollment process, the collection of data and specimens, and to analyze the results of bacterial culture, biomarkers, rapid diagnostic tests, molecular and serogical assays.

It is expected that the gold standard measurements will fall into three categories: confirmed viral (33%), confirmed bacterial (20%), and mixed/unconfirmed (47%). For purposes of algorithm development and assessment, we will combine the latter two groups (confirmed bacterial and mixed/unconfirmed) into a single group. The justification for the grouping is that clinically, a patient who receives a mixed/unconfirmed diagnosis will likely be treated in the same manner as a patient with a confirmed bacterial diagnosis.

As this is a preliminary study, we will fit the data using a variety of different approaches for combining diagnostic tests, including classification and regression trees, random forests, and multivariate logistic regression. For models with binary outputs, we will calculate the sensitivity and specificity (defined using confirmed bacterial as "cases" and confirmed viral as "controls"). For models with continuous outputs, we will calculate the receiver operating characteristic (ROC) curve. The relative performance of the models will primarily be evaluated based on sensitivity and specificity. 10-fold cross-validation or similar methods will be used to account for potential over optimism from fitting multiple models.

While clinical relevance is of primary importance, we may also consider algorithms that perform three-category classifications (with the categories as originally defined), as such results may be of etiologic interest. Furthermore, for all analyses, we may consider calculating the positive predictive value (PPV) and negative predictive value (NPV); while sensitivity and specificity are of primary importance, PPV and NPV may provide further useful descriptive information.

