- Comply with all study procedures including to store required specimens for diagnostic testing and archiving.

Exclusion criteria

- Being Hospitalized for more than 24 hours at enrollment
- Having a cancer or history of cancer
- Having a history of long term exposed of steroid (at the minimum of 2 months)
- Having any condition that might interfere with study procedure and compliance (based on clinicians' judgement)

Study Procedures
Participants who meet the inclusion and exclusion criteria will be enrolled and then having a daily follow up for maximum of 13 days' hospitalization. Next follow up will be taken time at day 14 th after hospitalization date, either on ward or polyclinic. The participations will be ended by day 30 th after hospitalization date when the called follow up is done by the Research Assistant (RA).
This study will collect demographic data, medical history, clinical data, treatment, and risk factors of pneumonia. The study also recorded the supporting examination results include but not limited to Complete Blood Count (CBC) results, blood gas analyses result, CRP, PCT, culture result, rapid test for influenza, Respiratory Syncytial Virus (RSV), legionella, and chest X-ray. In order to produce a robust data, this study will conduct the serological and molecular tests at the reference laboratory.
Whole blood, serum, urine, Nasal Pharyngeal Swab (NPS), sputum/induced sputum, and other respiratory specimens (if available) will be collected for storage and testing at enrollment. Any left-over respiratory specimens and/ or plasma on day 2 and 3 of hospitalization will also be collected to be stored. For additional, at day 14 th after hospitalization serum will be processed from 4 mL of blood for archiving and testing at the reference laboratory.

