3.2. Secondary Objectives

- To identify the etiologies of pneumonia in children in Indonesia, which are currently unavailable.
- To document outcomes in pediatric patients with pneumonia in Indonesia.
- To evaluate the performance of each rapid point of care test (to detect influenza and viral syncytial viruses, legionella urinary antigen, biomarkers of bacterial infections (CRP and PCT), and standard of care procedures (Chest X-ray, O₂ saturation, CBC, blood Gas Analyses (if available) compared to the gold standard molecular assays in differentiating virus and bacterial infections.
- To analyze the performance of combined tests in differentiating virus and bacterial infections.
- To provide information regarding updated strains of circulating respiratory viruses and pathogens in children.

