3.6.7. Laboratory procedures for Molecular and Serological Testing

This study will carry out molecular and serological testing that will be done at the reference laboratory. The study will cover all the costs of those tests.

Table 1 and Table 2 will furtherly explain the required specimen volume and tests needed. Also see appendix A for the work flow.

Table 1. The research specimen and laboratory testing

Visit /Time	Collected Specimen	Amount	Laboratory Testing at	
			Hospital	Reference Lab
Enrollment (up to 24 hours after enrollment)	Whole Blood	2 x 1 ml – 2 ml blood 1 x 3 ml blood	Blood culture (2 sides) CBC	PCR (Streptococcus pneumonia, Staphylococcus aureus, Haemophilus influenza)
	Serum	1 x 4 ml blood	CRP, Procalcitonin, HIV (can be done up to 5 days after enrollment)	Serology IgM and IgG (Influenza A, B, RSV, Parainfluenza virus, Adenovirus, Mycoplasma pneumonia, Chlamydia pneumonia, Bordetella pertussis, Legionella pneumonia)
Enrollment (up to 48 hours after enrollment)	Urine	1 ml – 3 ml urine	Rapid test Legionella antigen	PCR (Legionella pneumoniae, Leptospira)
	Nasopharyngeal swab	2 VTM (1.5 ml)	Rapid test Influenza Rapid test RSV	PCR (18- Viral Panel)
	Sputum/induced sputum	2 ml	Culture, MTB (genexpert, if AFB positive)	PCR (11 Bacterial and 18 viral panel)
	Other resp specimen (leftover – effusi pleura, BAL)	If available	Culture, MTB (genexpert, if AFB positive)	PCR (11 Bacterial and 18 viral panel)
Daily study visit during hospitalization	Left-over respiratory specimen and/or plasma (Daily study visit day 1 & 2 (day 2 & 3 of hospitalization)	If available	None	TBD
Study Visit Day 14th after hospitalization	Serum	4 ml blood	None	Serology IgM and IgG (Influenza A, B, RSV, Parainfluenza virus, Adenovirus, Mycoplasma pneumonia, Chlamydia pneumonia, Bordetella pertussis, Legionella pneumonia)
Follow-up Day 30 th after hospitalization	None	None	None	None

NOTE: Maximum amount of blood drawn in pediatric patients weight 7.3 – 45.5 kgs is 10 ml - 30 ml at any one time or 60 ml – 350 ml cumulative during hospitalization or maximum 1 month (Garza D, Becan-McBride K).

Table 2. PCR Panel for Bacterial & Viral Pathogens

PCR Viral Panel	PCR Bacterial Panel
Human Influenza A virus	Haemophilus influenza
Human Influenza B virus	Streptococcus pneumoniae
Adenovirus	Legionella pneumoniae
Enterovirus	Mycoplasma pneumoniae
Respiratory Syncytial Virus A	Chlamydia pneumoniae

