6.3. Operational Definitions

- Fever : temperature recorded $\geq 37.5^{\circ}\text{C}$ during the first 24 hours period of hospitalization or at home.
- Study specimens: specimens collected from study subjects.

- Respiratory samples: leftover respiratory samples (BAL, pleural fluid, etc) that are collected by the attending physician based on clinical presentation.
- Study clinical data: clinical data collected from study subjects.
- Study completion: Subjects followed until 30- days (\pm 4-days window period) after hospitalization or die.
- Subject withdrawal: if the subject's parents or legal guardians decides to voluntarily discontinue participation or the study physician decides to terminate subject participation at any time during the study.
- Missed visit: a scheduled study visit which a study subject fails to attend or a home visit does not occur.

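### Could a child with a positive blood culture or bacterial serology be counted as a confirmed viral control because Section 6.2 does not say which tests set the labels?

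*Combined protocol and SAP*

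**What the plan says.** Section 6.2 states that "It is expected that the gold standard measurements will fall into three categories", with expected shares of 33% confirmed viral, 20% confirmed bacterial and 47% mixed/unconfirmed. For building the algorithm, "we will combine the latter two groups (confirmed bacterial and mixed/unconfirmed) into a single group". For accuracy the contrast is narrower: confirmed bacterial children are the cases and confirmed viral children are the controls.

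Section 6.2 does not list the tests behind these labels. The section headed "6.3. Operational Definitions" defines seven terms, none of them one of the three categories. A standard is named only in a secondary objective (Research Summary and Section 3.2), where each rapid test, biomarker and routine procedure is to be "compared to the gold standard molecular assays in differentiating virus and bacterial infections".

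The study also gathers bacterial evidence by other routes. Section 4.6.2 plans blood culture for all participants. The Research Summary says "this study will conduct the serological and molecular tests at the reference laboratory", and Table 1 schedules serology at enrolment and day 14. The sentence in 6.2 just before the three categories says the interim reviews are "to analyze the results of bacterial culture, biomarkers, rapid diagnostic tests, molecular and serogical assays".

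**The concern.** If the phrase about molecular assays governs the algorithm's labels, the reference standard is lopsided. In Table 1 the nasopharyngeal swab receives "PCR (18- Viral Panel" only. The 11-bacteria panel is run on sputum or on leftover pleural or lavage fluid. A child with none of these is tested by PCR for every panel virus but for few panel bacteria.

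Take a child with RSV on the swab, no sputum, and *K. pneumoniae* in blood culture. If only molecular results count, the child is a viral control. If culture counts, the child is mixed. An algorithm that flags this child as bacterial would be scored wrong under the first reading. In model fitting the child would also change sides, because mixed is pooled with bacterial. A cultured organism outside the 11 targets raises the same question even when sputum is available. The labels feed the primary objective, and the algorithm is to be evaluated in a larger study.

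**Working it through.** **The plan's own precision figure.** Section 4.4 gives N = 275 and a 95% interval for each pathogen's prevalence no wider than ±7%. The worst case is 1.96 × √(0.25/275) = 5.9 points, so the statement holds.

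**Expected group sizes (shares from 6.2).** Viral 0.33 × 275 = 91; bacterial 0.20 × 275 = 55; mixed/unconfirmed 0.47 × 275 = 129. The pooled group is 55 + 129 = 184.

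**PCR coverage without sputum, pleural fluid or lavage fluid (Table 1 against Table 2).**
- Viruses: 18 of 18, from the swab.
- Bacteria: 3 in blood (*S. pneumoniae*, *S. aureus*, *H. influenzae*) plus *Legionella* in urine = 4 of 11. *Leptospira* is also tested in urine but is not a panel target.
- Serology adds *M. pneumoniae*, *C. pneumoniae* and *B. pertussis*, giving 7 of 11. The other four (*C. psittaci*, *M. catarrhalis*, *K. pneumoniae*, *B. pseudomallei*) have at most blood culture.

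**Effect of misplaced controls.** Suppose k of the 91 controls have a positive culture or serology and the algorithm calls a share p of them bacterial. With true specificity s, apparent specificity is [s(91 − k) + (1 − p)k]/91, so the loss is k(s − 1 + p)/91. The values of k, p and s are assumptions.

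| k | s = 0.80, p = 1 | s = 0.80, p = 0.5 | s = 0.90, p = 1 | s = 0.90, p = 0.5 |
|---|---|---|---|---|
| 3 | 2.6 points | 1.0 | 3.0 | 1.3 |
| 5 | 4.4 | 1.6 | 4.9 | 2.2 |
| 9 | 7.9 | 3.0 | 8.9 | 4.0 |

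The sampling half-width, 1.96 × √(s(1 − s)/91), is 8.2 points at 0.80 and 6.2 at 0.90. Only one of the 12 entries exceeds it: 8.9 against 6.2.

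**A child positive only by culture, with no virus.** This child is either confirmed bacterial or unconfirmed. Both fall in the pooled group, so model fitting does not change. Only the sensitivity denominator of about 55 moves. Its half-width at 0.80 is already 1.96 × √(0.16/55) = 10.6 points.

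**What a stricter control definition would cost.** Suppose virus-positive children without the respiratory bacterial panel were moved to mixed/unconfirmed. If 9, 23 or 46 of the 91 lacked it (assumed):
- controls fall to 82, 68 or 45;
- the half-width becomes 8.7, 9.5 or 11.7 points at 0.80 (6.5, 7.1 or 8.8 at 0.90);
- the moved children make up 9/193 = 5%, 23/207 = 11% or 46/230 = 20% of the enlarged pooled group.

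**The two uses of the gold standard, side by side.** Section 3.2 attaches molecular assays to the performance of each single test. Section 6.2, which serves the algorithm, uses the broader word *measurements*, directly after naming culture, molecular and serological results. It also has a category called mixed, which has meaning only if some bacterial finding takes a virus-positive child out of the viral group.

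**The case for a change.** The strongest case for a change is that the labels determine the primary result and no readable passage defines them. Section 6.2 even refers back to categories as if they had been defined. Mislabelling is systematic: neither cross-validation nor a larger sample removes it, so lying inside a sampling half-width does not make it harmless. A rule chosen after models have been fitted could favour one of them. Counting culture and serology needs no new test. Missing sputum is foreseeable, since the specimen-collection text in Section 5 makes testing depend on availability.

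The textual part stands: the readable text gives no explicit rule, and the coverage counts are exact. The harm is less secure. It requires carrying a phrase from a secondary objective into the primary analysis and then ignoring a positive blood culture when a mixed category is at hand. Table 1 refers the reader to Appendix A, whose chart is not visible here; its surviving caption mentions study outcome analysis. Other detail is left to the Manual of Procedures. Sputum or induced sputum is a planned enrolment specimen, and compliance with study procedures is an inclusion criterion (Section 4.5.1).

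A bacterial infection that no test detects is a separate matter, and no wording of the labels repairs it. If 5% or 10% of controls had one, with sensitivity and specificity both 0.90, apparent specificity would be 0.95 × 0.90 + 0.05 × 0.10 = 0.86, or 0.90 × 0.90 + 0.10 × 0.10 = 0.82. Requiring the full panel of controls would address part of this. But it would select controls by sputum availability while asking nothing similar of cases, who can be confirmed from blood. It would also put truly viral children into the group treated as positive in model fitting.

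**Conclusion.** No change to the plan follows. This is an unwritten detail that analysts would fill sensibly: a child with a virus and a credible positive bacterial culture or serology is mixed, not confirmed viral. Deciding which growth is a contaminant and which antibody result counts is ordinary laboratory reading, suited to the Manual of Procedures.

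The possible size is a loss of 1.0 to 8.9 points of specificity for 3 to 9 misplaced controls out of 91, with 11 of 12 scenarios inside the half-width of 8.2 or 6.2 points. These counts are assumptions, since the documents do not say how many children would be positive only by culture or serology or would lack a respiratory specimen. Section 4.4 calls the study preliminary, disclaims power for diagnostic accuracy, and leaves evaluation of the algorithm to a larger study.

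Requiring the respiratory panel of every control is a trade-off with no clear gain, for the reasons shown above.

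The conclusion rests on 6.2 being read in its ordinary sense. It would change if the Appendix A chart or the Manual of Procedures said that only PCR results set the labels.

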4.4. Population and Sample Size

This is a preliminary study to characterize the pathogens present in this cohort. The number of participants' that will be enrolled is based on the number of pneumonia cases in 5 years old children or less. This study plan to enroll with total of 275 participants.

With 275 participants, the 95% confidence interval for the prevalence of each pathogen will be no greater than $\pm 7\%$. The study is not powered to test the diagnostic accuracy of the algorithm. The algorithm developed from this study will be evaluated in a larger study, powered to estimate sensitivity and specificity. As a result, no formal power calculations have been provided.

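### Section 6.2 names logistic regression without a penalty or a rule for sparse tests; on the planned 184 v 91 fit this risks overfitting and possibly no finite weight for the Legionella test

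*Combined protocol and SAP*

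**What the plan says.** Section 4.4 gives the sample size: "This study plan to enroll with total of 275 participants". It calls the study preliminary, says that it is not powered for the accuracy of the algorithm, and defers that evaluation to a larger study.

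Section 6.2 expects the reference standard to give 33% confirmed viral, 20% confirmed bacterial and 47% mixed or unconfirmed. For developing and assessing the algorithm, "we will combine the latter two groups (confirmed bacterial and mixed/unconfirmed) into a single group". Sensitivity and specificity are then computed on confirmed bacterial children as cases and confirmed viral children as controls. A three-category model is optional.

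The methods are "classification and regression trees, random forests, and multivariate logistic regression", introduced as examples of several approaches. Models are compared mainly on sensitivity and specificity, with ROC curves for continuous outputs. Against overfitting the section says: "10-fold cross-validation or similar methods will be used to account for potential over optimism from fitting multiple models".

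Sections 3.2 and 4.3 name the candidate tests: rapid tests for influenza, RSV and Legionella, CRP, PCT, chest X-ray, oxygen saturation, blood count, and blood gas where available. Section 6.2 has no predictor list, no statement on penalisation, no rule for sparse or empty cells, and no calibration measure.

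**The concern.** Logistic regression fitted by maximum likelihood has two weaknesses in data of this shape. With few children per predictor it overfits, so predicted probabilities lie too close to 0 and 1. And if a yes/no test is positive in only one of the two classes (an empty cell), its weight has no finite estimate. Software then reports a very large number or a convergence warning.

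Cross-validation shows the cost of overfitting but repairs neither problem. It can also add empty cells: if a test has a single positive in one class, the training set that leaves that child out has none.

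The algorithm is the primary objective and is meant to go into a larger study. What goes forward is a set of weights and probabilities, so an infinite or badly inflated weight is a poor thing to hand over.

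**Working it through.** **The plan's own figures.** The only precision statement, in section 4.4, concerns pathogen prevalence: 1.96 × √(0.25/275) = 5.9%, within the stated ±7%. It does not bear on the algorithm. The class sizes follow from section 6.2:

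- viral 0.33 × 275 = 90.75, about 91
- bacterial 0.20 × 275 = 55
- mixed/unconfirmed 0.47 × 275 = 129.25, about 129
- merged class 55 + 129 = 184

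**Predictors.** Counted as named, there are 9: three rapid tests, CRP, PCT, X-ray, oxygen saturation, blood count, blood gas. Splitting the blood count into about 5 items and the blood gas into about 4 gives 3 + 4 + 5 + 4 = 16 (an assumption). In the planned fit the smaller class is the 91 viral children: 91/9 = 10.1 and 91/16 = 5.7 children per predictor.

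**Influenza and RSV in the planned fit.** Let f be a rapid test's false-positive rate, which the documents do not give. The chance that one viral test has no positive among the 55 bacterial children is (1−f)^55. If 2% of the 129 mixed/unconfirmed children test positive, the chance of none in the merged class is (1−f)^55 × 0.98^129:

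| f | none in 55 | none in merged 184 |
|---|---|---|
| 0.5% | 76% | 5.6% |
| 1% | 58% | 4.2% |
| 2% | 33% | 2.4% |

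If 5% of the mixed/unconfirmed children are positive, the last column falls to 0.1% or less. If they had false positives only, it would be (1−f)^184 = 40%, 16% and 2%.

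**Legionella in the planned fit.** Separation needs exactly one empty class. With a = (1−f)^91 and b = (1−f−0.9π)^184, where π is Legionella prevalence in the merged class and 0.9 an assumed sensitivity, the chance is a + b − 2ab. At f = 1% and π = 1%: a = 0.401, b = 0.981^184 = 0.029, giving 0.41. Over π = 0 to 2%, the chance is 53–63% at f = 0.5%, 40–43% at 1%, 16–18% at 2% and about 1% at 5%. If both classes are empty, the test is constant and simply drops out.

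**Cross-validation.** At f = 1%, the chance of at most one Legionella positive among 91 viral children is 0.99^91 + 91 × 0.01 × 0.99^90 = 0.77. Multiplying by the chance of some positive in the merged class, at 1–2% positivity (1 − 0.99^184 = 0.84; 1 − 0.98^184 = 0.98), gives 65–75%. In those cases at least one training fold is likely to separate.

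**Confirmed groups only, 55 v 91.** The chance that influenza or RSV has no positive among the 55 is 1 − (1−p)², with p = (1−f)^55: 94%, 82% and 55% at f = 0.5%, 1% and 2%. Adding Legionella (1% of bacterial children truly positive), at least one of three tests has an empty cell with probability 97%, 90% and 68%, and about 16% at f = 5%.

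**Simulated effect on predictions.** Assumed effect sizes, 16 predictors, performance measured in new data:

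- Planned 184 v 91, 300 data sets per setting, f = 0.5–2%: median slope 0.59–0.70, with 1–2% of predictions below 0.01 or above 0.99. In data sets with no empty cell the slope was still 0.65–0.75. With 10 predictors and f = 1% it was 0.71.
- Planned 184 v 91, other assumed effects, f = 1%, tuned ridge as comparator: empty cell in 64% of data sets; slope 0.52 unpenalised v 1.13 ridge; log loss 0.618 v 0.579; AUC 0.697 v 0.701; sensitivity + specificity − 1, 0.407 v 0.414.
- 55 v 91, f = 0.5–2%: median slope 0.35–0.44, with 15–21% of predictions below 0.01 or above 0.99.

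**The case against.** The plan is preliminary, claims no power for accuracy, and ranks models by sensitivity, specificity and ROC curves, not by calibration. Logistic regression is one of three named methods in an open list; trees and random forests do not separate. The wording does not exclude a penalty. With nine predictors there are about 10 children per predictor. All of this is fair. It makes the point an improvement rather than an error, and it means that the choice of best model on the plan's own criteria would hardly be affected. In one simulation with a fixed ridge penalty, sensitivity + specificity − 1 was slightly worse with the penalty (0.37 v 0.40). With the penalty tuned by cross-validation that loss did not recur.

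A reader might infer something stronger: that the main model is fitted to 55 bacterial v 91 viral children, that influenza and RSV will usually separate, and that one positive rapid test will then settle the class with certainty. Section 6.2 does not support this. It merges the mixed/unconfirmed children into the bacterial class for development, and mixed infections put viral positives on both sides. The 55 and 91 serve as the groups for sensitivity and specificity, and would be separate model classes only in the optional three-category analysis. A reader might also infer that cut-offs would not carry over to the larger study; the simulations do not show that.

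What stands is that the section leaves the predictors, the fitting method and the handling of a rare test open, and that the most literal reading is an unpenalised fit.

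**Conclusion.** The point holds as a cheap improvement. On the planned fit, an unpenalised model with about 16 predictors would be moderately overfitted, with a calibration slope of about 0.5 to 0.7. Most of that is ordinary overfitting, since it persists without any empty cell. The Legionella weight may have no finite estimate, in roughly 15% to 65% of data sets at false-positive rates of 0.5–2% and rarely at 5%. Influenza and RSV separation is a serious prospect only if the confirmed groups are fitted as separate classes. There, at least one of the three rapid tests has an empty cell with a chance from 97% down to about 16% over rates of 0.5–5%. Ranking, sensitivity and specificity change little either way.

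These sizes rest on assumptions that the documents do not settle: the count of 16, an unpenalised fit, the specificity and positivity of the rapid tests, and the simulated effect sizes.

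**What to change.** In section 6.2, list the candidate predictors and replace the unqualified logistic regression with a penalised one: ridge or LASSO with the penalty tuned inside each training fold, or Firth's method. Apply the same rule to the three-category model if it is fitted. Report the cross-validated calibration slope next to the ROC curve.

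The cost is a sentence or two and slightly more analysis work in standard software. Coefficients will be shrunk, which is intended. Ridge slopes somewhat above 1 (1.13 in the simulation above) show that it can over-shrink a little, which the reported slope would reveal.

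### Section 6.2 gives two conflicting case groups; if only confirmed bacterial children are scored, co-infected children drop out and the sensitivity cost of a viral rapid-test branch is understated

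*Combined protocol and SAP*

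**What the plan says.** Section 6.2 of the combined protocol and SAP expects 33% of children to be confirmed viral, 20% confirmed bacterial and 47% mixed or unconfirmed. It pools the last two groups for both development and assessment, because clinicians would probably treat them alike.

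The next paragraph, on models with a binary output, gives sensitivity and specificity as "defined using confirmed bacterial as 'cases' and confirmed viral as 'controls". These two measures are the main basis for comparing models. ROC curves are planned for continuous outputs, with no case group stated. Three-category classification and predictive values are optional, and no population is named for the predictive values.

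Table 1 (section 3.6.7) lists "Rapid test Influenza Rapid test RSV" at the hospital on the nasopharyngeal swab, with the 18-virus PCR on the same specimen at the reference laboratory. Table 2 shows influenza A and B and RSV A and B on that PCR panel. Section 3.2 sets out to judge each rapid test "compared to the gold standard molecular assays in differentiating virus and bacterial infections".

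The available text does not state the rule that assigns a child to a category. The Appendix A workflow figure is not shown.

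**The concern.** The pooling sentence makes a co-infected child a case. The sentence that defines the metric leaves that child out of both cases and controls. A statistician following the metric definition would rank models on children labelled purely viral or purely bacterial.

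This matters most for the viral rapid tests, because they seek viruses that the reference PCR also seeks. A child with PCR-detected influenza or RSV would naturally be labelled confirmed viral or, with a bacterium as well, mixed. On the confirmed-only contrast, such a child can hardly appear among the cases. A branch that sends rapid-test-positive children to the viral side gains specificity, and its cost in missed bacterial disease falls mainly on children who are not scored.

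Section 6.2's reason for pooling treats a mixed child like a bacterial one. By that reasoning, calling a co-infected child viral is an error that should count. Ten-fold cross-validation does not help, because it corrects for overfitting and does not change who is scored.

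**Working it through.** **Figures from the plan.** Section 4.4: "This study plan to enroll with total of 275 participants". The only precision figure there is a 95% half-width of at most 7 points for pathogen prevalence. At a prevalence of 50%, 1.96 × √(0.25/275) = 5.9 points, so that statement holds, but it does not bear on accuracy. Category counts from section 6.2:

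- viral: 275 × 0.33 = 90.75, about 91
- bacterial: 275 × 0.20 = 55
- mixed/unconfirmed: 275 × 0.47 = 129.25, about 129

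**Who is scored.** Confirmed-only: 55 + 91 = 146 of 275 (53%), leaving 129 (47%) out. Combined: 55 + 129 = 184 cases against 91 controls.

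**Assumed inputs (none is in the documents).**

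- 40% of virus-positive children have influenza or RSV.
- The rapid test has 70% sensitivity and 98% specificity against PCR.
- Positivity does not depend on bacterial co-infection.
- Confirmed bacterial and unconfirmed children have no virus detected.
- Half of the 129 are truly mixed (65 mixed, 64 unconfirmed), varied to 32 and 97 mixed.

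Positivity in virus-positive children = 0.40 × 0.70 + 0.60 × 0.02 = 0.292. In virus-negative children it is 0.02.

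**Rule examined.** Rapid test positive means viral; negative means bacterial group. Sensitivity = 1 − (rapid-test-positive cases ÷ all cases). Central case:

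- Confirmed-only: 1 − (55 × 0.02)/55 = 98%.
- Combined: 1 − (55 × 0.02 + 65 × 0.292 + 64 × 0.02)/184 = 1 − (1.10 + 18.98 + 1.28)/184 = 1 − 21.36/184 = 88.4%.
- Bacterial plus mixed: 1 − (1.10 + 18.98)/120 = 83.3%.

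| Truly mixed | Confirmed-only | Combined 184 | Bacterial + mixed |
|---|---|---|---|
| 32 | 98% | 93.3% | 88.0% |
| 65 | 98% | 88.4% | 83.3% |
| 97 | 98% | 83.7% | 80.6% |

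Specificity is 29.2% in every cell (26.6 of 91). The confirmed-only figure does not move with the amount of co-infection.

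**What the rule says within virus-positive children.** By assumption, positivity is 29.2% with or without a bacterium, so the likelihood ratio there is 1.0. The confirmed-only contrast would still show 0.292/0.02 = 14.6. The combined group gives 0.292/(21.36/184) = 2.5.

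**Bacteria among rapid-test positives.** Central case: (1.10 + 18.98)/(26.57 + 18.98 + 1.10 + 1.28) = 20.08/47.93 = 42%. On confirmed-only children: 1.10/(26.57 + 1.10) = 4%.

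**Wider ranges.** Take false positives of 0% to 5%, positivity in virus-positive children of 30% to 60%, and 25% to 75% of the 129 truly mixed. Sensitivity is then:

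- confirmed-only: 95% to 100%
- combined: 66% to 95%. Lowest: (55 × 0.95 + 96.75 × 0.40 + 32.25 × 0.95)/184 = 66%. Highest: (55 + 32.25 × 0.70 + 96.75)/184 = 95%.
- bacterial plus mixed: 60% to 89%. Lowest: (55 × 0.95 + 96.75 × 0.40)/151.75 = 60%. Highest: (55 + 32.25 × 0.70)/87.25 = 89%.

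**The case against.** The strongest reply is the pooling sentence itself. It covers assessment, so the metric definition may be loose shorthand for the combined group. On that reading, a rapid-test-positive co-infected child is scored as a missed case. This stands: the documents do not settle which sentence governs, and a reader cannot infer that mixed children will certainly go unscored. Even so, the pooled figure of 88% blends 98% in virus-negative children with 71% (1 − 0.292) in mixed children, so results by stratum are needed on either reading.

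Models are also to be developed with mixed children on the bacterial side, so fitting already penalises the branch. With 65 mixed, the rapid-test-positive node holds 26.6 viral against 21.4 bacterial-group children. With 97 it holds 26.6 against 30.1, and a majority-label tree would not call it viral. This stands too, and limits the fault to scoring and model comparison.

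Three stronger inferences are tempting but unsupported:

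- *A positive rapid test is scored correct by construction.* The reference is molecular, and the rapid test is not stated to be part of it. A false positive in a bacterial child counts as an error (about 0 to 3 of 55 at rates of 0% to 5%). A positive in a mixed child is at most unscored. Viral PCR also covers sputum and other respiratory specimens, and viral serology is done, so the viral evidence is not confined to one swab.
- *Models using rapid tests are favoured on sensitivity.* Calling more children viral cannot raise sensitivity. The branch gains specificity, and its sensitivity cost is understated.
- *Bacterial cases are virus-free by definition.* This is plausible because mixed is a separate category, but no visible rule says so.

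Finally, section 4.4 states: "The study is not powered to test the diagnostic accuracy of the algorithm". That concerns precision. It does not answer a question about who is scored, and this study produces the algorithm that the larger one will evaluate.

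**Conclusion.** The point holds as an inconsistency in section 6.2 with a consequence for model comparison. If the metric definition governs, 129 of 275 children go unscored and a viral rapid-test branch shows almost no sensitivity cost: 98% in the central case, against 88% on the combined group and 83% on bacterial plus mixed. If the pooling sentence governs, the understatement largely disappears, but performance in co-infected children stays hidden in the pooled figure.

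The direction follows from the category structure, provided that a virus plus a bacterium is read as mixed. The size does not follow from the documents. It rests on the assumed rapid-test positivity, its independence from co-infection, and the split of the 47%. The metric definition is written for binary-output models, and section 6.2 does not say that single-test performance under section 3.2 uses the same contrast, so the point should not be extended to that objective without clarification.

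**What to change.** In section 6.2:

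1. Reconcile the two sentences. For model comparison, calculate sensitivity, specificity and ROC on the combined bacterial plus mixed/unconfirmed group against confirmed viral.
2. Report sensitivity separately for confirmed bacterial, mixed and unconfirmed children. Keep confirmed bacterial against confirmed viral as a secondary contrast.
3. State the rule that assigns a child to each category, or point to where it is given.
4. Report the proportion with a bacterium detected among all children with a positive influenza or RSV rapid test, and among all children the algorithm calls viral.
5. Optionally, show in a descriptive table how well the rapid tests, CRP, PCT and chest X-ray separate virus-only from virus-plus-bacterium children. This need not be a model-selection rule.

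The cost is revised wording and a few tables from data already collected. The downsides are real: reported sensitivity will look less favourable, the combined group contains unconfirmed children of uncertain status, and the mixed stratum depends on how bacterial detection is read.
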